3.5.2 Behavioral Evaluations

Behavioral evaluations assessed by ACASI and interviewer administered questionnaires include;

- Frequency of unprotected sex (self-report of penetrative sexual intercourse since previous visit)/report of condom use
- Risk behaviors – including any new sexual partners/ encounters, concurrent sexual partners (stable or casual), alcohol/drug use, domestic violence e.t.c.
- HIV/STI risk perception and motivation to utilize RH and pregnancy related services
- Reproductive intentions and family planning
- Male partner/s involvement – presence, cohabitation, economic, psychosocial support, health care support, gender based violence etc

3.5.3 Psychological Assessments

The following psychological assessments will be conducted at enrolment (baseline), 3 months & at study exit;

- Psychosocial risk assessment using the HEADDSS assessment instrument
- Self-esteem assessment using the Rosenberg self-esteem scale[35]
- Psychological wellbeing using Ryff's scale[36] of psychological wellbeing

3.5.4 Clinical Evaluations and procedures

This involves history taking, physical and/or pelvic exams and other evaluations as indicated.

History Taking

- Demographic information is obtained
- Risk assessment during pregnancy to rule out any maternal problems (medical and obstetric history and update this history as appropriate)
- Postpartum, obtain history on any maternal problems (medical, gynecological (including symptoms of STIs) and contraceptive use history and update as appropriate)

Physical Exam:

- General physical exam – signs of anemia, BP, weight, breast
- Obstetric exam during pregnancy
- Additional clinical assessments may be performed at the discretion of the examining clinician in response to symptoms or illnesses present at the time of the exam

Other procedures which shall be done as indicated: prescribe contraceptives, provide available test results and provide treatment/referral as appropriate

3.5.5 Laboratory Evaluations

- Urine (25mls)
 - Urine dipstick for protein and glucose
 - HCG for pregnancy (5mls)
 - Rapid test for Gonorrhea infection (10mls)
 - Rapid test for Chlamydia infection (10mls) Blood (4mls)
 - 2mls for HIV serology (using national algorithm) [37]
 - Hemoglobin Concentration (Hb) by Hemocue ®
 - 2mls for RPR for syphilis (TPAB if positive)

Throughout the study duration, the total amount of blood collected from each participant will be about 10mls. Pelvic

 - Rapid test for Trichomonas
- Bacterial Vaginosis Testing – PH, Clue Cells, whiff test and homogenous abnormal vaginal discharge.

Bacterial vaginosis will be diagnosed using the following Amsel criteria. The presence of three of the following four criteria provides sufficient evidence for a clinical diagnosis of BV.

 - a) Vaginal pH >4.5 ((normal range 3.8 to 4.5)
 - b) The presence of clue cells (bacterial clumping upon the borders of epithelial cells) on wet mount examination. Clue cells should constitute at least 20% of all epithelial cells (an occasional clue cell does not fulfill this criteria).
 - c) Positive amine, "whiff" or "fishy odor" test (liberation of biologic amines with or without the addition of 10% Potassium Hydroxide (KOH)).
 - d) Homogeneous, nonviscous, milky-white discharge adherent to the vaginal walls
- Vaginal fluid for testing presence of Y chromosomes sequences. This is to validate women sexual behavior reporting whether there was unprotected sex in last 14 days.

3.5.6 Retention

Once a participant is enrolled and randomized into the study, the study staff must make every effort to retain her in follow-up to minimize possible bias associated with loss-to-followup. Standard operating procedures (SOPs) for participant retention to target loss-to-follow-up rates less than 10% shall be developed. As such, the average retention rate of 95% will be targeted for this study. All study staff are responsible for implementing local SOPs to achieve this. Components of such procedures may include the following:

- Thorough explanation of the study visit schedule and procedural requirements during the informed consent process and re-emphasis at each study visit. Also as part of the informed consent process, encouragement of participants to discuss potential study participation with their husbands/partners and other influential family members or persons.
- Thorough explanation of the importance of all study groups to the overall success of the study.
- Collection of detailed locator information at the study screening and enrolment visits, and active review and updating of this information at each subsequent visit.
- Use of mapping techniques to establish the location of participant residences and other locator venues.
- Ensuring ongoing contact with the study participant including soon after delivery and reminders about scheduled study visits

3.6 Study Endpoints

3.6.1 Quantitative data outcomes

Primary outcomes

1. Incidence of one or more STIs during study follow-up, with STIs confirmed by laboratory tests of HIV-1, Neisseria Gonorrhoea, Treponema pallidum (Syphilis), Chlamydia trachomatis, Bacterial Vaginosis or Trichomonas vaginalis (Composite outcome)
 - New HIV-1 diagnosis by 2 separate HIV tests with negative HIV-1 test at enrollment AND/OR
 - New Neisseria Gonorrhoea, Treponema pallidum (Syphilis), Chlamydia trachomatis, Bacterial Vaginosis or Trichomonas vaginalis test having been negative at enrollment OR with completed treatment if positive at baseline
2. Reported (and validated) consistent condom use and uptake of effective contraceptive method (Composite outcome)
 - Absence of repeat pregnancy (diagnosed by rapid urine pregnancy testing for HCG)
 - Uptake of effective contraceptive method with insertion/prescription by clinic staff from 3 months postpartum to 9 months or study completion (which ever comes 1st)
 - Self-reported consistent use of condoms during penetrative anal or vaginal sex including a) since enrollment b) since last visit c) at last penetrative sex act
 - Absence of Y-chromosome in analysis of vaginal swabs

Secondary outcomes

3. Acceptability/desirability of assigned clinic service model

Acceptability of clinic service model (composite)

- Frequency of visits
- Relevance of information to own life
- Sense of psychosocial support

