2 RESEARCH AIMS AND OBJECTIVES

AIM 1: To assess health care provider and adolescent mothers' Knowledge, Attitudes and Practices (KAP) regarding adolescent reproductive health and related health services and explore adolescents' risk perception and motivation to utilize reproductive health services and use of dual protection methods.

Objective 1.1: To describe health workers knowledge, attitudes and practices about the provision of adolescent reproductive health services as well as their perceptions of barriers to adolescent uptake of services and health promoting behaviors.

Objective 1.2: To describe adolescent knowledge, attitudes and practices in relation to their own reproductive health and uptake of health services and explore adolescents' sexual risk perception and motivation and use of dual protection methods.

AIM 2: To compare the effectiveness of adolescent peer group support and education, one to one peer support and education and routine care to help pregnant adolescents aged 15 to 19 years to achieve effective family planning and reduce STI incidence through 6 to 9 months post-delivery. STIs to be evaluated will include HIV, Gonorrhea, Syphilis, Chlamydia, Bacterial Vaginosis and Trichomoniasis.

Note: Routine care currently includes PMTCT services with HIV C&T and Uganda Ministry of Health messages given by midwives about healthy pregnancies during antenatal visits, and reproductive health at the 6 week postnatal visit; with referral for family planning for interested women.

Objective 2.1: To describe and compare baseline demographic and clinical characteristics of the study participants at enrollment by arm.

Objective 2.2: To describe and compare incidence of one or more STIs (including HIV) during study follow-up by study arm.

Objective 2.3: To describe and compare uptake of dual prevention methods (contraceptive services and condom use) during study follow-up by study arm

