For normal uncomplicated pregnancies, pregnant mothers are usually scheduled to have 4 routine visits during pregnancy; at 10–20 weeks, 20–28 weeks, 28–36 weeks and >36 weeks. At all these visits, risk assessment, fetal growth monitoring, health education and plans for delivery are made by nurses/midwives with referral to clinicians/obstetricians (where clinically indicated and available). Risk assessment is done by history taking, examination including blood pressure and weight measurement and investigations (recommended routine laboratory investigations include RCT, RPR for syphilis, Hb, urine for albumin and glucose). Other tests are recommended as appropriate for the individual patient to assess maternal well-being, e.g. ultrasound, amniotic fluid, fetal heart/movements)

Health promotion/education is usually delivered in group sessions by the nurses/midwives and issues discussed include; involvement of husbands in ANC, delivery plans, discuss future FP, discuss symptoms of miscarriage, pregnancy-induced hypertension (PIH), education and counseling on PMTCT of HIV and malaria prevention and use of insecticidetreated bed-net (ITN), education on danger signs in pregnancy, proper nutrition, adequate hygiene, breastfeeding and breast care, sexual activity during pregnancy, dual protection for FP/HIV, avoidance of smoking and alcohol and any problems are addressed.

Postpartum, the mother is counseled on contraception and appropriate method provided if required, mother is advised to abstain from sexual activity for at least 6 weeks after birth, mother is asked if both her and baby are sleeping under ITN (encouraged if not), new born hygiene and baby care, she is also advised on when to seek care as follows: scheduled infant immunizations 6 and 10 weeks, 3, 6, 9 and 12 months postpartum and at other times should the baby fall sick.

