3.7.2 Statistical analysis

Exploratory data analysis will be conducted on all variables including the binary outcomes. Descriptive statistics will be generated providing proportions (percentages) for categorical data, and mean (SD)-for normally distributed data, and median (IQR) nonnormal continuous variables. A consort diagram will also be generated to show the time of enrollment, and follow-up. Bar charts showing the distribution of categorical data will also be generated. Data will be assessed for missingness especially as a result of non-follow-up in this prospective study design. In order to address this concern, a comparison of non-follow-up and those followed up will be done, and propensity scores will be constructed to use as weights in the regression models. For categorical/dichotomous outcomes, we will use Fishers Exact Test or chi-square as appropriate, and will report the respective 95% confidence intervals around point estimates, which offer important interpretation for the trial findings.

Primary outcome-1: Composite measure of consistent condom-use and use of an effective FP method. A comparison of this binary outcome will be conducted at the last follow-up. A log-

binomial regression model will be used to obtain the prevalence rate ratios (PRR) as the measure of effect or association, because the outcomes are greater than 10%. The primary exposure variable is study arm. The two intervention arms will be compared to the control arm in the same model. Potential confounders will be adjusted for, after assessing for interaction of some variables with the study-arm in the association with the primary composite outcome. Respondents from the same facility may be correlated, and so adjustment for potential clustering of observations within the selected facilities will be done.

Primary outcome-2: Incidence of any STI. Kaplan-Meier survival analysis will be conducted to determine differences in the probability of STI infection between study arms. Differences in the KM will be determined by log-rank test. Further analysis will be conducted using Poisson regression models to obtain incidence rate ratios (IRR) comparing the two intervention arms to the control arm in the same model. Potential confounders will be adjusted for, after assessing for interaction of some variables with the study-arms in the association with the incidence of STI. Adjustment for potential clustering of observations within the selected facilities will be done.

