APPENDIX B: SCHEDULE OF STUDY VISITS AND EVALUATIONS

	SCR/ ENR	36 weeks APT	Birth †	6 weeks PPT	10 weeks PPT	3 months PPT	6 months PPT	9 months PPT
ADMINISTRATIVE AND REGULATORY								

Obtain Informed Consent	X							
Assign a unique Participant Identification (PTID) number	X							
Asses and/or confirm eligibility	X							
Collect/review /update locator information	X	X	X	X	X	X	X	X
Randomization	X							
Provide reimbursement	X			X	X	X	X	X
Schedule next visit	X	X		X	X	X	X	X
INTERVENTION								
Enhanced Counseling Education Sessions/Routine care as provided	X			X	X	X	X	X
BEHAVIORAL								
Behavioral Assessments using IAQ and ACASI	X				X		X	X
Psychosocial Assessment	X							X
HIV pre and post test counseling	X					X		X
Provision of Condoms	X	X	X	X	X	X	X	X
Conduct Social harms assessment					X		X	X
CLINICAL								
Obtain/review and update RH and Medical History	X	X	*	*	*	*	*	X
Clinical Examination – Blood Pressure, Weight, Obstetric exam	X	X						
Prescribe contraceptives				X	*	*	*	*
Provide available test results	X	X		*	*	X	*	X
Provide treatment/referral as appropriate	*	*		*	*	*	*	*
LABORATORY								
Blood	HIV-1 Serology (rapid tests)	X					X	X
	Syphilis serology	X					€	X
	RPR (TPAB if positive)							
Urine	Protein and Glucose	X	X					
	Rapid test for Gonorrhea infection	X	*		*	*	*	X
	Rapid test for Chlamydia infection	X	*		*	*	*	X
	HCG test				*	*	*	X
Pelvic	Rapid test for Trichomoniasis (self collected vaginal swab)	X	*		*	*	*	X
	Collect Vaginal swab for Bacterial Vaginosis testing	x	*		*	*	*	X

Collect vaginal swab for testing presence of Y chromosome ‡								X
QUALITATIVE COMPONENT								
Serial In-depth Interview (SIDI)	X				X			X
Focus Group Discussion (FGD)	X							X
Single In-depth Interview (IDI)				*	*	*	*	*

X mandatory, *If indicated †only for intervention groups, € repeat at 6months if positive at enrolment, ‡done only at study exit for participants with self reported condom use.

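### Primary outcome 2: the contraceptive component is dated by insertion or prescription from 3 months in one section and by use at last follow-up in another, so women protected at exit can be scored as failures

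*Combined protocol and SAP*

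**What the plan says.** **Endpoint definition (Section 3.6.1, primary outcome 2).** The contraceptive component is "Uptake of effective contraceptive method with insertion/prescription by clinic staff from 3 months postpartum to 9 months or study completion". The condom component is self-reported consistent use, "including a) since enrollment b) since last visit c) at last penetrative sex act".

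**Analysis (Section 3.7.2).** The same outcome, numbered primary outcome 1 there, is a "Composite measure of consistent condom-use and use of an effective FP method". The timing is given as: "A comparison of this binary outcome will be conducted at the last follow-up". Section 3.7.1 also sizes the trial on this composite at last follow-up.

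**Aim (Section 2, objective 2.3).** The general aim is to compare "uptake of dual prevention methods (contraceptive services and condom use) during study follow-up by study arm".

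**Schedule.** In Table 1 and Appendix B, the row "Prescribe contraceptives" is mandatory at 6 weeks postpartum and if indicated at 10 weeks and at 3, 6 and 9 months. Section 3.1 gives the 6- and 10-week study visits to Arms 2 and 3 only. Table 2 puts the control arm's first study visit after enrolment at 3 months postpartum.

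**Routine care.** The note under Aim 2 in Section 2 lists "reproductive health at the 6 week postnatal visit; with referral for family planning for interested women". The description of postpartum routine care in Section 3.4.6 says "the mother is counseled on contraception and appropriate method provided if required".

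**The concern.** An insertion or prescription dated from 3 months onward is not the same event as use at the last visit. A woman who receives a long-acting method at 6 weeks and still has it at exit fails the first test, read literally, and passes the second. She is also a foreseeable case, since the only visit at which the schedule makes prescribing mandatory falls before the window opens.

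This is a primary outcome. Two competent analysts could score it differently from the same data, and the choice could be made after the data are seen. Because the early study visits exist only in the intervention arms, any misclassification need not be equal across arms, so it could move the ratio as well as cost power.

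The condom component has a smaller version of the same gap: three windows are listed and nothing says whether all, any or one of them decides.

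**Working it through.** **1. Scoring three hypothetical women under the two wordings**

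| Woman | 3.6.1, literal (dated from 3 months) | 3.7.2 (use at last follow-up) |
|---|---|---|
| Implant at 6 weeks, in place at exit | failure | success |
| Method started at 4 months, stopped at 7 months | success | failure |
| Method started at 6 weeks, stopped before 3 months | failure | failure |

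The wordings disagree on the first two women, in opposite directions. A re-prescription in months 3 to 9 would rescue an early starter under 3.6.1, so the loss is surest for a single early insertion.

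**2. The plan's own figure**

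Section 3.7.1 gives 71 control and 50 per intervention arm for this composite (10% versus 30% and 35%, 80% power, 5% type 1 error, 10% loss). The control figure follows from 50 × √2 = 70.7. The 50 does not follow from all the stated inputs: a two-sided pooled calculation for 10% versus 30% gives about 73 and 52 before allowing for loss, and about 82 and 58 after. Nothing below depends on this, because the trial enrols 215 and 152.

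**3. Size of the date-rule effect (illustration)**

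Inputs from Section 3.7.1: true success 30% (one intervention arm) versus 10% (control); 10% loss to follow-up. Evaluable: 152 × 0.9 = 137 and 215 × 0.9 = 194 (rounded).

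Assumptions not in the documents: the share of true successes lost because the method was dated only before 3 months, Li in the intervention arm and Lc in control.

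Observed ratio = [0.30 × (1 − Li)] / [0.10 × (1 − Lc)] = 3.0 × (1 − Li)/(1 − Lc).

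Power is for a result favouring the intervention: Pearson chi-square, two-sided 5%, exact enumeration.

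| Li | Lc | Observed rates | Ratio | Power |
|---|---|---|---|---|
| 0 | 0 | 30.0% v 10.0% | 3.0 | 99.6% |
| 25% | 25% | 22.5% v 7.5% | 3.0 | 97.5% |
| 50% | 50% | 15.0% v 5.0% | 3.0 | 89% |
| 50% | 25% | 15.0% v 7.5% | 2.0 | 61% |
| 25% | 50% | 22.5% v 5.0% | 4.5 | 99.8% |

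Equal loss leaves the ratio unchanged and power above the planned 80%. Unequal loss moves the ratio either way.

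**4. Condom windows**

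Consistency since enrolment normally implies consistency since the last visit and at the last act. Requiring all three therefore reduces to the since-enrolment window, and accepting any reduces to the last act. Only the since-last-visit window depends on the visit schedule, and the documents conflict on that schedule. The text of Section 3.1 gives all three groups a 6-month visit, while the Arm 1 row of Table 1 marks only enrolment, 3 months and 9 months. If the Arm 1 row is followed, this window for a month-9 exit is 9 − 3 = 6 months in control and 9 − 6 = 3 months in the intervention arms.

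**The case against.** **The 3.6.1 line may mean use during months 3 to 9.** That reading is possible and would remove most of the conflict. No section adopts it, and the words attach the period to insertion or prescription. The ambiguity stands.

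**The 3-month start may be deliberate.** Month 3 is the first postpartum study visit common to all arms, which is a sensible reason to begin there. It explains when assessment starts, but does not justify failing a woman still protected at exit. Table 3 also lists prescribing at 36 weeks antepartum and as indicated, which softens the mandatory 6-week mark.

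**Objective 2.3 is not a rival scoring rule.** Correct. It states a general aim, and the conflict that matters is between 3.6.1 and 3.7.2.

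**Stronger readings the documents do not support.** A reader might infer that the date rule works against the intervention arms, because only they have early study visits. Routine care also provides methods postpartum and refers at 6 weeks, so the net direction cannot be known. A reader might also infer that unequal condom recall windows favour the intervention arms. That needs two conditions together: the since-last-visit window alone decides, and controls have no month-6 assessment. No section states the first. The second rests mainly on the Arm 1 row of Table 1, against the 3.1 text and the behavioural entries for month 6 in Table 1, Table 3 and Appendix B. False-positive rates computed under both conditions are not evidence of bias in this trial.

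**The loss shares are assumptions.** They are, and the 61% comes from one unequal pair among many possible ones.

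**Conclusion.** The point holds for the contraceptive component. Sections 3.6.1 and 3.7.2 give different tests for the same primary outcome, and the literal 3.6.1 test can fail women who are protected at exit. That misclassification follows from the wording; its frequency and its balance between arms do not, since the documents give no share of methods started before 3 months.

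On the assumed shares, the consequence runs from a modest power loss with an unchanged ratio of 3.0 to a ratio anywhere from 2.0 to 4.5. This should be fixed before analysis, but it does not show bias in a known direction. The condom point is secondary: an unstated choice among listed windows, with no demonstrated artefact.

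**What to change.** **Contraceptive component.** Define it as current use of an effective method at exit, whatever the start date, ascertained by the same method in all arms at the exit visit. Use the clinic record of insertion or prescription as support, including any renewal needed for the method to cover the exit date. Put the same wording in 3.6.1 and 3.7.2.

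**Condom component.** Before analysis, name one deciding window of equal calendar length in all arms, asked at exit. Do not let the since-last-visit window decide alone. If since enrolment, or all three together, is chosen, state that it includes the roughly 4 weeks before the first session (Table 2) and so may dilute the effect.

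**Schedule.** Reconcile the 3.1 text with the Arm 1 row of Table 1 on the control arm's 6-month visit.

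**Cost.** Outcome wording and possibly one questionnaire item, with no new visits. The main burden is that records of early methods for controls must be sought from routine clinics, where Section 3.4.6 admits that practice varies. Relying on clinic records is already built into 3.6.1, and asking every woman about current use at exit limits how far uneven records can affect the arms differently.

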We will conduct a 3-arm, randomized, controlled trial of 519 pregnant adolescents aged 15 through 19 years at enrollment to test the acceptability and effectiveness of two enhanced adolescent friendly reproductive health prevention interventions versus current routine care. In each intervention group, 152 adolescent mothers will be randomized to either the enhanced group peer support education and counseling intervention or to the enhanced one-to-one (individual) peer support education and counseling group with a young, model, peer educator trained to deliver RH education and counseling messages, beginning during pregnancy (≥ 28 weeks) and followed up to 9 months postpartum or study end at or after 6 months (whichever comes first). The control group will consist of 215 adolescent mothers randomized to routine care as provided at Mulago hospital (or the designated health facility) where midwives deliver group sessions during antenatal and postpartum care visits as well as standard PMTCT services including routine opt-out HIV C&T and availability of partner C&T. Syphilis testing should also be routinely provided and treatment provided for infected pregnant mothers and their partners as per local standard of care.

The 3 groups will be enrolled with study visits at 3, 6 and 9 months post-partum however the intervention groups (Arms 2 and 3) will have additional visits at 36 weeks Antepartum, delivery, 6 and 10 weeks postpartum, Quantitative baseline data will be collected on routine demographic characteristics, reproductive history, pregnancy intentions and sexual risk/perceptions and HIV/STI status.

Summarized table 1 of the study schedule and evaluation

	SCR/ ENR	36 weeks APT	Birth†	6 weeks PPT	10 weeks PPT	3 months PPT	6 months PPT	9 months PPT†
Arm 1– Routine Care	X					X		X
Intervention: Enhanced Counseling Education Sessions/Routine care as provided	X			X	X	X	X	X
Behavioral Assessments using IAQ and ACASI	X				X		X	X
Psychosocial Assessment	X					X		X
Obtain/review and update RH and Medical History	X	X	*	*	*	*	*	X
Clinical Examination – Blood Pressure, Weight, Obstetric exam	X	X						
Prescribe contraceptives				X	*	*	*	*
Provide available test results	X	X		*	*	X	*	X
Provide treatment/referral as appropriate	*	*	*	*	*	*	*	*
LABORATORY								
Blood	HIV-1 Serology (rapid tests)	X					X	X
	Syphilis serology RPR (TPAB if positive)	X				€		X
Urine	Protein and Glucose	X	X					
	Rapid test for Gonorrhoea infection	X	*		*	*	*	X

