	Urine	 Collect Urine (20mls) 
  Rapid test for Gonorrhea infection  Rapid test for Chlamydia infection
	Pelvic	
 • Collect vaginal swab for rapid Trichomonas vaginalis testing • Collect swab for Bacterial vaginosis testing (PH, Whiff and Clue cells)

Enhanced Peer Support Education and Counseling (Intervention)	Depending on the group the participant is randomized to, the intervention will be done around 4 weeks after enrolment as this is logistically appropriate for the study. Participants in Arm 2 will be put in homogenous groups (similar gestation, age group and language preference) of 8 – 12 adolescents, while the Arm 3 participants will schedule their individual follow-up visits on the same day as their clinic visits. Participants in the Control Arm will receive routine antenatal, delivery and follow-up services with next study visit at 3 months postpartum
Qualitative component	Participants preselected for the serial IDIs and FGDs will have the baseline interviews and FGDs within 3 weeks of enrolment prior to receiving the intervention

The participant will be provided with an appointment card (usual cards used in the ANC/PNC clinics) however a round colored sticker (different colors for each study arm) will be placed on the card to differentiate the 3 study groups.

STI treatment will be provided for any curable STI diagnosed at screening and in follow-up for the participant and her partner/s in accordance with national treatment algorithms.[33-34] Participants found to be HIV positive (by two separate rapid tests) will not be excluded from this proposed study but will be counseled, encouraged to disclose to their partner/s and will receive PMTCT services including Option B+ with ARV treatment for life as per national guidelines. As part of PMTCT services they will be encouraged to invite their partner/s for HIV C&T and their HIV-exposed infants will be followed up with linkages to ongoing services. Participants with positive syphilis tests will be treated and have repeat testing done per local national guidelines and also at the final visit.

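### If condom use is scored since the last visit, Table 1's control row gives controls a 6-month window at a 9-month exit against 3 months in Arms 2 and 3

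*Combined protocol and SAP*

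**What the plan says.** Section 3.6.1 defines primary outcome 2 as a composite of reported and validated consistent condom use and uptake of effective contraception. Four elements are listed under it: no repeat pregnancy, contraceptive uptake, self-reported consistent condom use, and no Y chromosome on the vaginal swab. The condom element is "including a) since enrollment b) since last visit c) at last penetrative sex act". No scoring window is named.

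Section 3.5.2 describes the behavioural item as "Frequency of unprotected sex (self-report of penetrative sexual intercourse since previous visit)/report of condom use". Section 3.7.2 analyses the composite at the last follow-up with a log-binomial model. That model has no term for the length of the recall window.

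The visit schedule is stated in more than one way:

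- In Table 1 (section 3.1) the row "Arm 1– Routine Care" is marked at enrolment, 3 months and 9 months. The row "Enhanced Counseling Education Sessions/Routine care as provided" is marked at enrolment, 6 and 10 weeks, and 3, 6 and 9 months.
- The text above Table 1 says "The 3 groups will be enrolled with study visits at 3, 6 and 9 months post-partum".
- The behavioural assessment row of Table 1, repeated in Appendix B, marks month 6 as mandatory and names no arm. Table 3 (section 3.5.1.1) lists behavioural assessment at 3, 6 and 9 months, also without naming an arm.

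**The concern.** Consistent use means no unprotected act during the window, so a shorter window is easier to satisfy. If the window runs back to each woman's own previous visit, and visits are spaced differently by arm, then the outcome is not the same measure in each arm. The error would favour both intervention arms on a primary outcome.

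Nothing else in the plan would remove it. By section 3.5.5 the Y-chromosome swab checks only the last 14 days, and it is taken at exit from women who report consistent use. It cannot correct a difference between 3 and 6 months.

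**Working it through.** **Sample sizes.** Section 3.7.1 gives 215 controls and 152 per intervention arm (215 + 152 + 152 = 519). These are not disputed. After the plan's 10% loss, 215 × 0.9 = 193.5 and 152 × 0.9 = 136.8, taken as 194 and 137.

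**Window length at exit, since the last visit.**

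| Schedule read from | Exit month | Arm 1 | Arms 2 and 3 |
|---|---|---|---|
| Table 1, Arm 1 and session rows | 9 | 9 − 3 = 6 months | 9 − 6 = 3 months |
| Text above Table 1, or Table 3 | 9 | 9 − 6 = 3 months | 9 − 6 = 3 months |
| Either | 6 (last to enrol) | 6 − 3 = 3 months | 6 − 3 = 3 months |

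So the windows differ only under the Arm 1 row, and only for women who leave at month 9. On the other schedule, a woman who misses month 6 still gets a 6-month window. The plan gives no attendance rates by arm.

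**Size with identical behaviour in all arms.** The documents give no condom-use rate for either window. I assume that 10% of controls are consistent over 6 months. That is the plan's control figure for the whole composite, borrowed here for the condom part. I then find the proportion P₃ consistent over 3 months and the chance that a two-sided 5% test of P₃ against 10% (137 v 194, pooled variance) shows a benefit. The nominal chance is 2.5%.

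- Constant, equal risk: P₃ = √0.10 = 31.6%.
- A share a of women always use condoms and the rest have constant risk: P₃ = a + (1 − a)√((0.10 − a)/(1 − a)). With a = 5%, this is 0.05 + 0.95 × √(0.05/0.95) = 26.8%.
- Gamma frailty with variance v: P₃ = ((1 + 0.10⁻ᵛ)/2)^(−1/v). With v = 4, this is 5000.5^(−1/4) = 11.9%.

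| Assumption | P₃ | Chance of false benefit |
|---|---|---|
| Constant risk | 31.6% | 99.8% |
| 5% always-users | 26.8% | 97.6% |
| 8% always-users | 21.6% | 82% |
| 9% always-users | 18.5% | 61% |
| Frailty, v = 1 | 18.2% | 57% |
| Frailty, v = 4 | 11.9% | 8% |
| All 10% always-users | 10.0% | 2.5% |

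**Allowing for the contraceptive part.** Let the 10% be the composite instead, with contraceptive uptake q independent of condom use. The control condom rate is then 0.10/q and the 3-month composite is q√(0.10/q) = √(0.10q). With q = 20% this is 14.1% (false benefit 22%). With q = 80% it is 28.3% (99%).

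**Month-6 exits dilute the effect.** As an illustration, if 25% leave at month 6 in the 8% always-user case, the control rate becomes 0.75 × 10% + 0.25 × 21.6% = 12.9%. The chance of a false benefit falls from 82% to about 55%.

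**The case against.** The strongest objection is that the bias needs two conditions together. Window (b) must score the outcome, and controls must have no month-6 assessment. Neither is established. Windows (a) and (c) do not depend on visit spacing. If all three had to be met, (a) would decide, because it contains the other two. On the second condition, the text above Table 1, Table 3 and Table 1's own behavioural row all point to a month-6 assessment in every arm. This stands, and it makes the point conditional.

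Three stronger readings are tempting and are not supported:

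- A reader might infer that a trial with no true effect would be significant 82% to 99.8% of the time. That range covers only constant risk with up to 8% always-users. It also treats the composite's 10% as the condom rate and assumes that everyone leaves at month 9.
- A reader might point to month 3, where Arms 2 and 3 were last seen at week 10 and controls at enrolment ("follow-up services with next study visit at 3 months postpartum"). The composite is analysed at the last follow-up, and Table 1 and Appendix B schedule no behavioural assessment at month 3.
- A reader might take the Table 3 footnote, which limits reimbursement and HIV testing to 3 months and exit, as proof that controls are seen less often. It is not specific to any arm.

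The objection does not remove the wording itself. The only recall period in section 3.5.2 is tied to the previous visit, section 3.6.1 repeats it as an option, and the control schedule that sets its length is contradictory.

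**Conclusion.** The concern holds in conditional form. As written, the plan allows a primary outcome to be scored on a window set by each woman's previous visit. One of its statements of the control schedule makes that window twice as long in controls (6 v 3 months) at a 9-month exit. If that schedule is followed and window (b) scores the outcome, the error favours both intervention arms.

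The size cannot be fixed from the documents. With 10% of controls consistent over 6 months, the same behaviour over 3 months gives 10% to 32%, and the chance of a false benefit per comparison runs from nominal to over 99%. The upper end is close to the 30% that the plan assumes as a real effect. Where the truth lies depends on how much condom use varies between women, on contraceptive uptake and on how many leave at month 6. The plan states none of these. If controls attend at month 6, the difference disappears for them.

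This should be fixed; confidence is moderate.

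**What to change.** Name one recall window in section 3.6.1 for scoring the condom element, the same in every arm and independent of which visits a woman attended. A fixed period such as the last 3 months at exit would do, as would the last sex act, which is already item (c). Reword the section 3.5.2 item and the matching questionnaire and ACASI questions to agree. Optionally add a 14-day item, so that self-report and the Y-chromosome swab cover the same period. Reconcile the Arm 1 row of Table 1 with the text above it, with the behavioural row and with Table 3, so that one control schedule remains.

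The cost is a change to a few questionnaire items and one endpoint line; the sample size is unaffected. The small drawback is that a fixed window leaves some exposure time uncounted. The change must come before data collection, because answers about the wrong period cannot be recovered later.
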